9.2 General statistical considerations

Statistical evaluation will be performed by the Sponsor or designee and supervised by the Exploratory Statistics Department of UCB. For safety analyses, data will be summarized by dose levels of rozanolixizumab at the time of the event or measurement. For efficacy, data will be summarized by the dose first received in the study. Additionally, efficacy data will be summarized by dose levels of rozanolixizumab received in each treatment cycle.

All analyses will be performed using Statistical Analysis System (SAS[®]) version 9.3 or later (SAS Institute, Cary, NC, USA). Continuous variables will be summarized by visit (where applicable) with the statistics including the number of study participants (n), mean, standard deviation (SD), median, minimum, and maximum. Categorical variables will be summarized by visit (where applicable) with frequency counts and percentages.

If not otherwise stated, Baseline values will be the last available predose value, or in the case of analyses done by 6-week treatment cycle, Baseline will be defined as the Baseline (Day 1) value for that cycle. This will be clearly defined in the SAP. All relevant data will be listed by treatment group and study participant.

9.2.1 Intercurrent event handling rationale and impact on the study

In MG0007, every study participant, except those coming from MG0004, will start with an initial fixed mandatory cycle. Prior to dosing in the initial fixed treatment cycle, the study participant will be assessed for MG worsening (eg, an increase of 2.0 points on the MG-ADL or 3.0 points on the QMG scale). The study participant will be initially randomized to rozanolixizumab equivalent to approximately 7mg/kg or 10mg/kg weekly (QW). After the first treatment cycle, dose adjustments may be applied at the start of each treatment cycle based on Investigator's discretion. Dose adjustments may not be applied during a treatment cycle.

For the assessment of safety and tolerability, adverse events (AEs) recorded up to 8 weeks after the last sc infusion will be utilized for main analyses, regardless of study participants receiving treatment with rescue therapy.

For the analyses of efficacy endpoints, the intercurrent events to be considered are the use of rescue therapy prior to Day 43 and permanent treatment discontinuation (or withdrawal from study) due to TEAEs. Efficacy endpoints will be summarized in line with a treatment policy approach. With this approach, rozanolixizumab results will be analyzed regardless of study participants receiving treatment with rescue therapy. Summaries will also be presented for the efficacy endpoints where participants will be censored at the time that they take rescue medication.

Missing values will not be imputed.

9.3 Planned safety analyses

9.3.1 Analysis of the primary safety endpoint

The frequency and severity of all TEAEs will be presented for each treatment group separately and overall by System Organ Class, high level term, and preferred term (Medical Dictionary for Regulatory Activities [MedDRA®]). The data will be displayed as number of participants experiencing the TEAE, percentage of participants, and number of TEAEs. All safety analyses will be based on the SS (Section 9.1).

For each cycle, a TEAE is defined as any event that was not present prior to the first administration of rozanolixizumab or any unresolved event already present before the first administration of rozanolixizumab that worsens in intensity following exposure to treatment up to and including 8 weeks after the last dose of each treatment cycle. Adverse events occurring after the 8-week TEAE period, prior to the next cycle, will be defined as intermittent period AEs. Any AEs that occurred during the study will be defined as "any AE".

The occurrence of TEAEs and TEAEs leading to withdrawal of IMP will be summarized for the entire study by dose at AE onset. This will include all TEAEs that occurred during and between treatment cycles.

These analyses will display the TEAEs (including any TEAEs occurring up to 1 week after the last infusion) and intermittent period AEs separately. For intermittent period AEs, the summaries will be displayed as "Off-treatment".

Further analyses will be described in the SAP.

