6.3 Measures to minimize bias: randomization and blinding

An interactive response technology (IRT) will be used for assigning eligible participants to a treatment regimen (as applicable) based on a predetermined production randomization and/or packaging schedule provided by UCB (or designee). The randomization schedule will be produced by the IRT vendor. The IRT will generate individual assignments for kits of study medication, as appropriate, according to the visit schedule. Study participants from MG0003 who complete the EOS visit will be rerandomized in MG0007. Randomization in MG0007 is to a ratio of 1:1. Study participants from MG0004 will not be rerandomized upon entering MG0007, but will continue their last treatment regimen received in MG0004 for their first treatment cycle in MG0007.

To enroll a study participant (Visit 1), the Investigator or designee will contact the IRT and provide brief details about the participant to be enrolled. Study participants will retain the same 5-digit number assigned at Screening in MG0003 that serves as the participant identifier throughout the study. The participant number will be required in all communication between the Investigator or designee and the IRT regarding a particular participant. Participant numbers and kit numbers will be tracked via the IRT.

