6.6 Dose modification

Dose modifications from 10mg/kg to 7mg/kg equivalent and vice versa is permitted at the beginning of the treatment cycles at the Investigator's discretion, and if the benefit-risk remains favorable for the study participant. Recommended dose modifications from 10mg/kg to 7mg/kg equivalent due to drug-related adverse events which may include but not limited to:

- Moderate to severe headaches that are considered to be related to rozanolixizumab
- Moderate to severe GI disturbances that are considered to be related to rozanolixizumab
- Moderate to severe toxicities (\geq Grade 2 as defined by Common Terminology Criteria for Adverse Events [CTCAE], version 5.0) for which rozanolixizumab cannot be excluded as a cause
- Recurrent hypogammaglobulinemia with a serum total IgG level of <2 g/L.

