3.6 Treatment assignment and treatment groups

For the analyses using SS, FAS and ES by entire study and first dose received, study participants will be grouped according to the highest dose levels of IMP participants received in MG0007 first cycle (7mg/kg or 10mg/kg). If participants switched dose in first cycle of MG0007, then they will be assigned to IMP 10mg/kg group. For example, if a participant's highest dose in first cycle of MG0007 is IMP 10 mg/kg and then changed to 7 mg/kg in the next cycle, then the participant will still be allocated to 10 mg/kg for these analyses.

For the safety analyses using SS by entire study and most recent dose received (summary of adverse events), participants will be grouped according to the most recent dose level of IMP participants received prior to the onset of AEs. For example, if a participant's last dose prior to an AE is 10 mg/kg, then the participant will be allocated to 10 mg/kg for this AE.

For the analyses performed using SS and FAS by treatment cycle, participants will be grouped according to the highest dose levels of IMP participants received (7mg/kg or 10mg/kg) within

each cycle. If participants switched dose within one cycle, then they will be assigned to IMP 10mg/kg group for that cycle. For example, if for a participant, the highest does in first cycle is 10 mg/kg and the highest dose received in second cycle is 7 mg/kg, then the participant will be allocated to IMP 10 mg/kg and 7mg/kg respectively.

For participants who were not treated in FAS and ES, they will be assigned to 'Not Treated' group.

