8.2.2 Adverse events summaries

TEAEs will be summarized by the most recent dose level prior to onset of TEAEs for entire study analysis or the highest dose within a cycle for by-cycle analysis and RLZ total including the number and percentage of study participants and frequency. Additional details are described below:

1. Overview of TEAEs by entire study and study cycle will include following categories: any TEAEs, serious TEAEs, participant discontinuation due to TEAEs, permanent withdrawal of IMP due to TEAEs, temporary withdrawal of IMP due to TEAEs, TEAEs requiring dose change, treatment-related TEAEs, severe TEAEs, TEAEs leading to death, all deaths (AEs leading to death). Additionally, summary of TEAEs by study cycle, fixed dose and weight subgroups will be conducted as specified in [Section 4.9.2](#).
2. Incidence of TEAEs will be summarized for entire study by SOC, HLT, PT for:
 - Any TEAEs
 - Any TEAEs during Treatment Period
 - Any TEAEs by maximum intensity (mild, moderate and severe)
 - Any TEAEs by relationship
 - Severe TEAEs

- Non-serious TEAEs above reporting threshold of 5% of study participants
- Fatal TEAEs
- Fatal TEAEs by relationship
- Serious TEAEs
- Serious TEAEs by relationship
- Participant discontinuation due to TEAEs
- TEAEs leading to permanent withdrawal of IMP
- TEAEs leading to temporary withdrawal of IMP
- TEAEs requiring dose change
- Treatment-emergent AESM
- Treatment-emergent AESI

3. Incidence of any TEAEs by entire study and study cycle will be summarized by decreasing participant count of PT in RLZ total. Same analysis will be repeated by fixed dose and weight subgroups as specified in [Section 4.9.2](#).

4. Incidence of TEAEs will also be summarized by SOC, HLT, PT, and the highest dose level prior to onset of TEAEs and RLZ total for each study cycle, including the number and percentage of study participants and frequency for:

- Any TEAEs
- Severe TEAEs
- Serious TEAEs
- Participant discontinuation due to TEAEs
- TEAEs leading to permanent withdrawal of IMP

5. Overview of non-TEAEs by entire study will include following categories: any non-TEAEs, serious non-TEAEs, participant discontinuation due to non-TEAEs, permanent withdrawal of IMP due to non-TEAEs, temporary withdrawal of IMP due to non-TEAEs, severe non-TEAEs, non-TEAEs leading to death.

6. Incidence of non-TEAEs will be summarized for entire study by SOC, HLT, PT for:

- Any non-TEAEs
- Severe non-TEAEs
- Serious non-TEAEs
- Fatal non-TEAEs

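### Entire-study TEAE tables by dose at onset mix dose with earlier tolerability, and no planned TEAE table isolates the participants randomised 1:1

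*Protocol*

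**What the plan says.** **Grouping.** Protocol 9.3.1 sets the entire-study rule for both primary endpoints: "The occurrence of TEAEs and TEAEs leading to withdrawal of IMP will be summarized for the entire study by dose at AE onset". SAP 3.6 repeats it: "participants will be grouped according to the most recent dose level of IMP participants received prior to the onset of AEs". SAP 8.2.2 groups TEAEs by "the most recent dose level prior to onset of TEAEs for entire study analysis or the highest dose within a cycle for by-cycle analysis".

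**Dose changes.** Protocol 6.6 opens with "Dose modifications from 10mg/kg to 7mg/kg equivalent and vice versa is permitted at the beginning of the treatment cycles at the Investigator's discretion". It continues: "Recommended dose modifications from 10mg/kg to 7mg/kg equivalent due to drug-related adverse events which may include but not limited to". The listed triggers are moderate to severe related headache, moderate to severe related GI disturbance, other toxicity of Grade 2 or higher, and recurrent IgG below 2 g/L. Protocol 9.2.1 bars dose adjustment within a cycle.

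**Allocation.** Protocol 6.3 states: "Randomization in MG0007 is to a ratio of 1:1". This covers MG0003 entrants. MG0004 entrants are not rerandomised and take their last MG0004 regimen into their first MG0007 cycle.

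**Other planned tables.** SAP 8.2.2 item 4 adds by-cycle tables of any, severe and serious TEAEs, study discontinuations, and TEAEs leading to permanent IMP withdrawal. SAP 8.2.3 adds AEs of focus by cycle. Markedly abnormal laboratory values, vital signs and ECG (SAP 8.3, 8.4.1, 8.4.2) are shown for the entire study by initial dose. TEAEs are not.

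**The concern.** A table by dose at onset describes what happened while people were on each dose. It compares doses fairly only if being on a dose is unrelated to the person's tendency to have AEs. In Cycle 1 that holds for MG0003 entrants, by randomisation. Later it need not hold. A participant with a drug-related AE on 10 mg/kg may be moved to 7 mg/kg, so recurrences fall in the 7 mg/kg column, while those who tolerate 10 mg/kg stay where they are. If upward moves go mainly to participants without AEs, the sorting is stronger.

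The columns will stand side by side for the primary endpoints, and readers will compare them. At stake is a misreading of how tolerability differs between the doses, when an unconfounded contrast could be had from the same data.

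**Working it through.** **1. Hand check of the mechanism.** The documents give no AE or switching rates, so these inputs are assumptions. Half the participants are AE-prone, with per-cycle risk 0.7 on 7 mg/kg; the rest have 0.2. Allocation is 1:1. Half of those with an AE on 10 mg/kg step down for the next cycle, and nobody moves up. Shares below are per one unit starting in each arm.

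*No true dose effect.* The Cycle 1 rate in each arm is 0.5 × 0.7 + 0.5 × 0.2 = 0.45. In Cycle 2:
- Still on 10 mg/kg: prone 0.5 × (1 − 0.7 × 0.5) = 0.325; others 0.5 × (1 − 0.2 × 0.5) = 0.450. Prone share 0.325/0.775 = 0.419. Rate 0.2 + 0.5 × 0.419 = 0.410.
- On 7 mg/kg: prone 0.5 + 0.175 = 0.675; others 0.5 + 0.05 = 0.55. Prone share 0.675/1.225 = 0.551. Rate 0.2 + 0.5 × 0.551 = 0.476.

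A gap of 0.410 v 0.476 appears although dose has no effect.

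*True risk ratio 1.25.* Risks on 10 mg/kg are 0.875 and 0.25, so Cycle 1 is 0.5625 v 0.45, a difference of 0.1125. In Cycle 2:
- Still on 10 mg/kg: prone 0.5 × (1 − 0.4375) = 0.281; others 0.5 × (1 − 0.125) = 0.4375. Prone share 0.281/0.719 = 0.391. Rate 0.25 + 0.625 × 0.391 = 0.495.
- On 7 mg/kg: prone 0.719, others 0.5625. Prone share 0.719/1.281 = 0.561. Rate 0.2 + 0.5 × 0.561 = 0.481.

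The true excess falls from 0.1125 to 0.014 after one round of step-downs.

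**2. More cycles.** This is the same model, simulated with 400,000 participants per scenario. Values are 10 v 7 mg/kg, with half of those affected stepped down. The last column assumes a denominator of participants ever on that dose.

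| True RR | Cycles | Move 7 to 10 without AE | Cycle 1 | All cycles, rate by dose at onset | Participants with at least one AE |
|---|---|---|---|---|---|
| 1.0 | 6 | 0 | 0.450 v 0.448 | 0.380 v 0.480 | 0.869 v 0.845 |
| 1.25 | 3 | 0 | 0.563 v 0.449 | 0.510 v 0.474 | 0.788 v 0.718 |
| 1.25 | 6 | 0 | 0.562 v 0.448 | 0.459 v 0.481 | 0.910 v 0.844 |
| 1.25 | 6 | 25% | 0.563 v 0.450 | 0.449 v 0.514 | 0.848 v 0.748 |

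The per-cycle rate can reverse. The participant percentage does not reverse here, because the AE that triggers a step-down stays under 10 mg/kg.

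**3. A second risk model.** Again the inputs are assumed: individual risk beta-distributed with mean 0.30 on 7 mg/kg, up to 5 cycles, 80% continuing to each next cycle, no moves from 7 to 10, true risk ratio 1.2.
- Strong variation (concentration 1), 50% step-down: Cycle 1 about +4.6 points; per-cycle by dose at onset about −8.9; participants with an AE 48.7% v 51.8%, so reversed.
- Moderate variation (concentration 3), 50% step-down: about +5.8; about −1.8; 59.2% v 56.6%, so not reversed.
- Moderate variation, 25% step-down: per-cycle 33.3% v 31.7%. The direction is kept, but the difference shrinks from about 5.9 to 1.6 points.

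**4. What the planned tables isolate.** By Protocol 9.2.1, the Cycle 1 dose should equal the randomised dose for MG0003 entrants. The by-cycle TEAE tables are not restricted to them, and neither document gives the MG0003/MG0004 split of the roughly 200 participants, so the dilution is unknown. The by-cycle label also varies within SAP 8.2.2: one place takes the highest dose in the cycle, while item 4 reads "Incidence of TEAEs will also be summarized by SOC, HLT, PT, and the highest dose level prior to onset of TEAEs and RLZ total".

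**5. Denominator.** A participant who has taken both doses can contribute to both dose-at-onset columns. Neither document says who makes up the denominator of each column.

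**The case against.** The study is descriptive. SAP 4.1 plans no testing, the primary objective concerns the safety of additional cycles, and each TEAE summary has a total column that switching cannot affect. MG0003 supplies blinded single-cycle data at the same doses. Grouping by dose at the event is declared openly, and SAP 8.1 tabulates treatment sequences and plots each participant's doses. All of this stands. No error rate is at risk, and the dose-at-onset tables are legitimate descriptions of exposure.

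A reader might infer more than the documents support:
- **That step-downs go uncounted.** SAP 8.2.2 tabulates TEAEs requiring a dose change, beside permanent and temporary withdrawal.
- **That intolerance on 7 mg/kg can only continue or end in withdrawal.** Protocol 7.1.3 provides temporary discontinuation without regard to dose.
- **That the randomised first cycle is unused.** By-cycle tables exist; the gap is the pooling with MG0004 entrants. Those participants were randomised in MG0004, but they enter on their last dose there, and exclusion 5a removes anyone who permanently discontinued.
- **That participants are routinely moved down.** The change is recommended and discretionary, and the reverse move is allowed.
- **That the primary result would be reversed.** The planned display is participants, percentages and event counts. In the scenarios above the percentage reversed only under strong between-participant variation.

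**Conclusion.** The concern holds in a limited form. After Cycle 1 the dose columns of the entire-study primary safety tables depend partly on earlier AEs, and no TEAE table isolates the 1:1 randomised comparison. The distortion bears most on event counts and per-cycle rates, and less on the participant percentage. With a true risk ratio of 1.2 to 1.25, the illustrative per-cycle contrast ranged from a reduced excess at 10 mg/kg to a reversal of about 9 points. These sizes rest on assumed AE risks, step-down probabilities and numbers of cycles; the direction of the sorting rests on Protocol 6.6 being followed. No figure in the documents is wrong. This is an inexpensive improvement to the reporting, and it does not undermine the study's overall safety summary.

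**What to change.** In SAP 8.2.2:
1. Add a Cycle 1 table set for MG0003 entrants in the Safety Set, by MG0007 randomised dose: any TEAE, TEAE leading to permanent IMP withdrawal, serious TEAE, AESM, and headache as an AE of focus. End the window at 56 days after the last Cycle 1 dose or at the first Cycle 2 dose, whichever comes first.
2. State that any safety comparison of 7 with 10 mg/kg rests on this set.
3. Define the column denominator of the entire-study dose-at-onset tables, including how a participant who took both doses is counted.
4. Footnote those tables: the 7 mg/kg column includes participants stepped down after AEs.
5. Use one by-cycle dose label throughout the section.

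The rows for permanent withdrawal and for dose change should be read together; a combined row is optional.

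The cost is SAP wording and a few tables from data already held (randomised allocation, entry study, AE records), with no change in conduct. The new set covers one cycle and MG0003 entrants only, so it is less precise and says nothing about later cycles. The dose-at-onset tables stay as descriptions of exposure.

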9.3.2 Other safety analyses

The occurrence of serious TEAEs and occurrence of treatment-emergent AESM will be summarized using the same approach as for the primary endpoints.

Laboratory evaluations and vital signs as well as ECG data will be analyzed over time. All safety analyses will be listed and summarized for the SS.

9.4 Planned efficacy and other analyses

9.4.1 Efficacy analyses

The main efficacy endpoint is the "Change from Baseline (Day 1) to Day 43 in MG-ADL score," for each of the first three 6-week treatment cycles where the Baseline of the respective cycle will be used as reference.

The summaries will be provided overall and by randomized treatment in-line with a treatment policy approach. Observed results will be presented for the different cycles (1 to n) regardless of the first cycle being mandatory or not. Missing values will not be imputed. Further summaries will be presented by the treatment received in each cycle.

The other secondary efficacy endpoints, Change from Baseline (Day 1) to Day 43 in QMG score, Change from Baseline (Day 1) to Day 43 in MG-C score, Change from Baseline (Day 1) to Day 43 in MG Symptoms PRO 'Muscle Weakness Fatigability' score, Change from Baseline (Day 1) to Day 43 in MG Symptoms PRO 'Physical Fatigue' score, and Change from Baseline (Day 1) to Day 43 in MG Symptoms PRO 'Bulbar symptoms' score, will be analyzed in the same way as the main secondary endpoint based on the MG-ADL.

Time to MG-ADL response (≥ 2.0 -point improvement from Baseline [Day 1]) for each treatment cycle will be summarized using time-to-event methodology (Kaplan Meier).

The time between consecutive treatment cycles will be summarized in order to provide information on how long the effect of rozanolixizumab lasts, ie, how long it will take to introduce a new cycle.

The number and percentage of participants achieving Minimal Symptom Expression (MG-ADL score of 0 or 1) at any time during the Treatment and Observation Periods will be summarized by cycle and by dose administration in that cycle.

Additionally, the number of treatment cycles will be summarized by treatment group.

Further summaries will be described in the SAP.

9.4.2 Other analyses

9.4.2.1 Pharmacokinetic analyses

Plasma concentration data of rozanolixizumab will be summarized by dose arm for each cycle, and time point using the number of available observations, mean, median, SD, minimum, maximum, geometric mean (and associated 95% confidence intervals), and geometric coefficient of variation (assuming log-normally distributed data) for the SS. Values below the lower limit of quantification (LLOQ) will be reported with a clear sign indicating that they were below the LLOQ. Descriptive statistics of concentrations will be calculated if at least two thirds of the

individual data points are quantifiable (\geq LLOQ). Individual and mean concentrations of rozanolixizumab may be displayed graphically.

Plasma concentration data of rozanolixizumab may be subjected to population pharmacokinetic analysis to derive population estimates of PK parameters and test the effect of various covariates such as anti-drug antibodies, age, weight, gender. Details of the analysis will be described in a separate Data Analysis Plan (DAP). This analysis may be performed by combining the data from the current study with data from other rozanolixizumab studies if deemed appropriate. The results of the population PK analysis will not be reported in the clinical study report (CSR) but in a separate modelling report.

9.4.2.2 Pharmacodynamic analyses

For all other endpoints relating to PD endpoints, descriptive statistics for the value, change from Baseline, and percentage change from Baseline will be tabulated by dose arm, and time point for the SS for each cycle. The PD endpoints will include serum total IgG, IgG subclass levels, and anti-MuSK and -AChR autoantibodies.

For the analysis of the IgG data, in case rescue therapies are taken, only the data up to the start date of rescue therapy will be utilized for the summary tables. Listings will contain all IgG data and the measurements of study participants, which have been excluded from the summary tables. In cases where a study participant drops out, no missing value imputation will be performed for the IgG. Absolute and relative IgG reduction for a cycle will be calculated with the cycle Baseline value as reference. As for safety, the IgG reduction analyses will be compared between cycles.

Population PD or population PK/PD analyses may be conducted for the PD variables of interest. Details of such PD or PK/PD analyses will be described in a separate DAP. The results of the analyses will not be reported in the CSR but in a separate report.

